This section outlines the statistical analysis strategy and procedures for the study. If, after the study has begun, changes are made to primary and/or key secondary hypotheses, or the statistical methods related to those hypotheses, then the protocol will be amended (consistent with ICH Guideline E-9). Changes to exploratory or other non-confirmatory analyses made after the protocol has been finalized, along with an explanation as to when and why they occurred, will be listed in the Clinical Study Report (CSR) for the study. Post hoc exploratory analyses will be clearly identified in the CSR. A separate Statistical Analysis Plan (SAP) with further details than presented here will be finalized prior to first patient enrolled to minimize any bias, as the study is non-blinded.

Power and Sample Size

The determination of sample size for this study is based on the primary objective to demonstrate the superiority of the IrriSept irrigation unit versus conventional standard of care in patients who undergo open abdominal laparotomy for abdominal trauma or acute surgical abdomen within 36 hours of initial presentation to their healthcare organization. The primary endpoint is the rate of SSI observed within 30 days (+/- 3 days) from the date of the index operation.

Based on historical data, it is assumed that the rate of SSI within the standard of care group will be \geq 20%. A total of 600 patients (300 per group) will provide \geq 90% power to demonstrate a reduction in the rate of SSI, up to 50%, assuming a control group rate for SSI of \geq 20%, based on a two-sided Chi-square test with a 5% significance level. The following table shows the power achieved under various combinations of control group SSI rates and relative treatment differences.

Table 2.1: Power associated with a total sample size of 600 (n=300/group), based on a two-sided Chi-square test with a 5% significance level.

Control Group SSI	Relative Treatment Difference (IrriSept/Control)		
Rate	50% Reduction	40% Reduction	30% Reduction
15%	83%	62%	38%
20%	93%	76%	50%
25%	98%	87%	61%

It is anticipated that approximately 1100 patients will be screened, 650 patients will be enrolled, to obtain 600 evaluable patients, based on a non-evaluable rate of approximately 5%. All calculations were carried out in SAS version 9.2 using the comparison for two independent proportions procedure in PROC POWER.

Study Number IRR-CT-901-2013-01	Version: 1.0	01AUG2014

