© Confidential IrriMax Corporation		Page 28 of 35

Analysis Populations

Intention-to Treat (ITT)

The intention-to-treat population will be defined as all randomized subjects. Subjects will be assigned to a group based on the group they were randomized to.

Per-Protocol Population (PP)

Within the ITT population, subjects will be considered evaluable if they completed the 30 day follow up visit. Subjects who are withdrawn from the study prior to the 30 day follow up will be designated "non-evaluable" and excluded from the PP population.

Safety Analysis Set (SAS)

The safety analysis set will consist of all randomized subjects who underwent an emergency operation. The safety analysis set will be used for all safety analyses. Subjects will be assigned to a group based on the actual procedure received.

Efficacy Analyses

Primary Endpoint

For the primary endpoint, the number and proportion of patients with a SSI observed within 30 days from the date of emergency operation will be summarized by treatment group, along with the difference and 95% confidence interval for the difference (based on the Wald method). If a patient is missing their end of study assessment, or if they died prior to the end of study assessment, they will be classified as having met the primary endpoint of a SSI. A comparison between treatment groups will be made using the Cochran-Mantel-Haenszal test, stratified by site. The two-sided p-value, the adjusted relative risk (IrriSept/Control) and 95% confidence interval of the relative risk (based on the Wald method) will be reported. The study will be deemed successful if the two-sided p-value for the end of study treatment difference is < 5%.

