Concomitant medications are medications that are taken at any time after enrollment. Concomitant medications will be coded using the WHO Drug Dictionary and summarized by drug class and preferred term for each treatment group. The summaries will present the number and percentage of patients using each medication in each treatment group. Patients may have more than one medication per preferred term. At each level of summarization, a patient is counted once if he/she reported one or more medications at that level.

Disposition

A clear accounting of disposition including, the number and percentage of patients screened, randomized, and completed, as well as the primary reasons for screen failure and reasons for early discontinuation of therapy will be reported overall and by treatment group.

Subjects who withdraw from the study (either voluntarily or involuntarily) or do not complete the required End of Study visit will be designated as "non-evaluable." Any data collected on these subjects will not be used in the final efficacy analysis. For those who withdraw consent, screen fail information will be collected. For those subjects lost to follow-up will be noted in the database as early termination. Subjects who are classified as "non-evaluable" will be replaced to the extent required to enroll 600 evaluable subjects.

Study Number IRR-CT-901-2013-01	Version: 1.0	01AUG2014
© Confidential IrriMax Corporation		Page 31 of 35

Interim Analyses

An interim analysis is planned when approximately 33% and 66% of the total number of patients has been enrolled. The purpose of these interim analyses is to monitor safety and study conduct. At the second interim analysis, the sample size will be re-estimated using the conditional power approach.

All persons involved in the conduct and analysis of the study will remain blinded to the results of the interim analysis.

Test Material Compliance and Accountability:

An initial supply of Study Product will be supplied to the study site, by IrriMax Corporation, at least one (1) week prior to study commencement.

Procedures and instructions for Study Product dispensing and accountability will be provided in the Investigator Site Binder.

Investigator Site Responsibilities:

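### The power statement claims at least 90% power for reductions below 50% that its own table does not support, and the sample size follows a missing-data rule that conflicts with the primary-endpoint rule

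*Combined protocol and SAP*

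**What the plan says.** **Power statement.** Power and Sample Size (under Statistical Methods) assumes a control SSI rate of at least 20%, 300 patients per group and a two-sided 5% chi-square test. It claims at least "90% power to demonstrate a reduction in the rate of SSI, up to 50" percent. Table 2.1 follows:

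| Control rate | 50% reduction | 40% reduction | 30% reduction |
|---|---|---|---|
| 15% | 83% | 62% | 38% |
| 20% | 93% | 76% | 50% |
| 25% | 98% | 87% | 61% |

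**Enrolment.** The same section says that "650 patients will be enrolled, to obtain 600 evaluable patients, based on a non-evaluable rate of approximately 5" percent.

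**Patients without a final assessment.** Two rules are given.

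- Efficacy Analyses, Primary Endpoint: if the end-of-study assessment is missing, or the patient died before it, "they will be classified as having met the primary endpoint of a SSI".
- Disposition: patients who withdraw or do not complete the End of Study visit are non-evaluable. "Any data collected on these subjects will not be used in the final efficacy analysis", and they "will be replaced to the extent required to enroll 600 evaluable subjects".

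**Populations and test.** Analysis Populations states: "The intention-to-treat population will be defined as all randomized subjects". Under the per-protocol definition, "subjects will be considered evaluable if they completed the 30 day follow up visit". The primary-endpoint text specifies the test ("A comparison between treatment groups will be made using the Cochran-Mantel-Haenszal test, stratified by site") but does not say which population it is applied to.

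**The concern.** There are two separate problems.

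1. A claim that covers reductions up to 50% also covers 40% and 30%. The plan's own table gives less than 90% power for both, at both control rates within the claim. A reader relying on the sentence would think the trial well powered for a 40% reduction from 20%, where the table gives 76%.

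2. The same patient cannot be both counted as an event and left out and replaced. The sample size is built on the second rule, while the first is the one written for the endpoint that decides success. If the first governs, adding a similar share of imputed events to each arm narrows the relative difference being tested, and 93% no longer describes the primary test. The trial is open-label, so the rule should not be left to be settled once outcomes are known.

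**Working it through.** **Step 1. Reproduce Table 2.1.** Inputs from Power and Sample Size: n = 300 per group, two-sided alpha 0.05 (z = 1.96), chi-square test. With control rate p1, treated rate p2 = p1 × (1 − reduction) and p̄ = (p1 + p2)/2:

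power = Φ{ [ (p1 − p2) − 1.96 √(2p̄(1 − p̄)/n) ] / √([p1(1 − p1) + p2(1 − p2)]/n) }

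For 20% v 10%: p̄ = 0.15, the standard errors are 0.02915 (null) and 0.02887 (alternative), and (0.10 − 1.96 × 0.02915)/0.02887 = 1.485. Power is 93.1%.

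| Control rate | 50% reduction | 40% reduction | 30% reduction |
|---|---|---|---|
| 15% | 83.0% | 61.9% | 37.9% |
| 20% | 93.1% | 76.3% | 49.9% |
| 25% | 97.7% | 86.7% | 61.3% |

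All nine cells match the plan to the nearest percent. Exact enumeration of the same test gives 93.5%, 76.7% and 49.9% at a 20% control rate, and 97.8%, 86.9% and 61.5% at 25%.

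**Step 2. Compare the sentence with the table.** Six cells have a control rate of 20% or more. Two reach 90% (93%, 98%) and four do not (76%, 50%, 87%, 61%). Solving the formula for 90% power at n = 300 gives a minimum reduction of 47.4% at a 20% control rate and 42.0% at 25%. A 47.5% reduction from 20% gives 90.1%.

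**Step 3. Which rule does the sample size follow?** At 5% non-evaluable, 600/0.95 = 631.6, so 632 randomised leave 600 evaluable. The 650 quoted implies 50/650 = 7.7%. Either way the power is computed on 600 completers with undiluted rates. That matches the Disposition rule, and no stated power figure contains imputed events.

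**Step 4. Illustration under the count-as-SSI rule.** The documents give no death or missing-visit rate. Assume a fraction m is imputed in each arm, equal in both and unrelated to SSI. Each observed rate becomes m + (1 − m)p.

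At m = 5%:

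- Control: 0.05 + 0.95 × 0.20 = 24.0%.
- Treated: 0.05 + 0.95 × 0.10 = 14.5%.
- Reduction as tested: 1 − 0.145/0.240 = 39.6%.
- 316 per arm (632): (0.095 − 1.96 × 0.03137)/0.03114 = 1.077, power 85.9%.
- 325 per arm (650): (0.095 − 1.96 × 0.03093)/0.03070 = 1.120, power 86.9%.

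For 20% v 10%, if enrolment stops at 600 evaluable, so that 600/(1 − m) are randomised:

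| m | Power |
|---|---|
| 0% | 93.1% |
| 1% | 91.8% |
| 2% | 90.4% |
| 3% | 88.9% |
| 5% | 85.9% |
| 7.7% (650 randomised) | 81.8% |

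Power crosses 90% at about m = 2.2% on this basis and 3.2% at a fixed 650, so no single threshold should be read from it.

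For 25% v 12.5% at m = 5%, the rates become 28.75% v 16.88%, and power is 94.7% (632) or 95.2% (650).

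**Step 5. Does stratifying by site change this?** The planned test was simulated with 12 and 14 equal sites, 1:1 within site, 100,000 runs each, for 20% v 10%. With no imputation and 600 patients, power was 93.4–93.5%. With 5% imputed it was 86.1–86.3% at 632 and 87.2% at 650. With a between-site SD of 0.5 on the logit scale, the 5% figures were 85.9–86.0% and 87.0–87.1%. Stratification does not alter the picture.

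**The case against.** **On the power sentence.** The table sits directly beneath it and prints the lower figures, so nothing is hidden. The sample size, alpha, test and all nine cells are right, so this is a drafting error and no design decision changes. That is fair as to kind. But the sentence is the stated power claim, and a correct table does not make it true.

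**On the missing-data conflict.** It is a separate matter and would exist even if the power sentence were perfect. The power loss is also conditional:

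- If the Disposition rule governs, 93% stands.
- The 5% is a non-evaluable rate, not a missing-outcome rate. Visit 2: End of Study allows telephone assessment and use of earlier standard-of-care visit data, which would lower the imputed share.
- If patients who die or miss the visit have SSI more often than others, some imputed events are real ones and the dilution differs from that shown.
- At a 25% control rate power stays well above 90% with 5% imputed.
- Interim Analyses plans a conditional-power re-estimation of sample size, though with no target power or maximum.

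All of this stands as a limit on the 86–87% figure, which is why it is only an illustration. None of it reconciles the two rules.

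**On the separate SAP.** The plan promises one with further details, and it might name the population. Nothing in the supplied text does, and a later document cannot be assumed to resolve two opposing rules already in the protocol.

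**On the 650.** Rounding 632 up to 650 is conservative. This is right, and the mismatch with 5% is clerical.

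**Conclusion.** Both parts hold.

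The power sentence is wrong as written. With 300 per group, 90% power requires a relative reduction of at least about 47.4% from a 20% control rate, or 42.0% from 25%. This rests only on the plan's own inputs.

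The plan also gives two incompatible rules for patients without a final assessment, does not say which population carries the primary test, and sizes the trial on the exclude-and-replace rule alone. That follows from the text and needs no assumption. How much power is lost is uncertain. With equal imputation in both arms, unrelated to SSI, at the plan's own 5%, power for 20% v 10% is about 86–87% instead of 93%. It is higher if fewer outcomes are imputed or the control rate is above 20%, and it is unchanged if the Disposition rule governs.

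These points should be corrected, but they do not call for a larger trial.

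**What to change.** 1. **Rewrite the power sentence** to match Table 2.1, for example: *300 evaluable patients per group give 93% power for a 50% relative reduction from a 20% control rate, 76% for 40% and 50% for 30%; 90% power needs a reduction of at least about 47.5%.* This wording describes the primary test only if non-evaluable patients are excluded, so finalise it together with item 2.

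2. **Reconcile the Primary Endpoint and Disposition sections** by naming one analysis population and one missing-data rule for the primary test.
   - If missing and dead patients are counted as SSIs, restate the power under that rule over a labelled range of imputed fractions.
   - If non-evaluable patients are excluded and replaced, Table 2.1 stands.

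3. **Clerical.** Align the 650 with the non-evaluable rate (7.7% as written, not about 5%). Also reconcile Study Sample Size, which describes the 650 as completing, with Power and Sample Size, which describes them as enrolled.

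Item 1 is a one-sentence edit. Item 2 is a decision on the primary analysis; the plan's own terms under Statistical Methods make it a protocol amendment once the study has begun. Neither adds patients. The cost is a less favourable stated power.

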This is a Phase IV, multi-center, prospective, randomized controlled, comparator clinical trial. Twelve to fourteen (12-14) Level I Trauma Centers throughout the United States will participate as research sites conducting this protocol. After the research site receives Institutional Review Board (IRB) approval, patients between the ages of 18-70 years old who undergo open abdominal laparotomy for abdominal trauma or acute surgical abdomen within thirty-six (36) hours of initial presentation to their healthcare organization may be eligible for study inclusion. Exclusion criteria includes: known allergy to chlorhexidine gluconate (CHG), Abbreviated Injury Scale (AIS) score of six (6), American Society of Anesthesiologists Physical Status Classification (ASA) score of five (5) or greater, female subjects who are pregnant and/or breast feeding, those patients undergoing a damage control laparotomy, a drain is placed within the wound or an intra-abdominal drain exits through the primary incision, reoperation occurs through the primary incision or transgresses the primary incision as the index procedure within 30 days, and those enrolled in a concurrent, ongoing interventional, randomized clinical trial.

Patient risk factors will be assessed at screening include chronic uncontrolled hypertension, chronic heart disease, chronic renal disease, chronic pulmonary disease, diabetes mellitus, HIV, chronic liver disease, a BMI of less than 18 or above 40, coagulopathy, current long-term steroid use, current smoker, and current cancer. Additional assessments include PATI (Penetrating Abdominal Trauma Index), AIS and ASA scores, and adherence to SCIP prophylactic antibiotic-specific guidelines. Other measures to be documented will include antibiotic used and surgical skin preparation used. The following present on admission (PoA) characteristics are documented: shock, (systolic BP < 90 mm Hg), intubation, active infection, transfusion of blood/blood products and primary injury in trauma or primary organ(s) in the acute abdomen. Intra-operative SSI risk factors including drains, staple versus sutures, surgical time (skin to skin), blood/blood products, and body temperature below 36°C are assessed and risk adjusted in the final analysis.

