- Recorded data from automated instruments such as (ECGs, rhythm strips, electroencephalograms (EEGs), pulmonary function tests, etc.)
- Records of telephone contacts
- Evaluations checklists
- Study Product distribution and accountability logs maintained by study personnel
- Correspondence between physicians or memoranda to IRBs/IECs regarding any subject's treatment

Statistical Methodology:

Endpoints

Efficacy

Primary

The primary efficacy endpoint is the rate of SSI observed within 30 days from the date of index operation.

Secondary

The secondary efficacy endpoints will include the following:

- The length of stay in the hospital
- Rate of readmission to the hospital, within 30 days from the date of the index operation
- Estimated costs of the index hospitalization

Exploratory Endpoints

The following outcomes will be reviewed as exploratory endpoints:

- Superficial surgical site infection (SSI)
- Deep surgical site infection (SSI)
- Organ/space surgical site infection (SSI)
- Ventilator associated pneumonia (VAP)
- Catheter associated urinary tract infection (CAUTI)
- Central line associated blood stream infection (CLABSI)
- Deep vein thrombosis (DVT)
- Pulmonary embolus (PE)
- Acute cardiac event

Study Number IRR-CT-901-2013-01	Version: 1.0	01AUG2014
© Confidential IrriMax Corporation		Page 27 of 35

- Clostridium difficile (C-diff) infection
- MRSA infection
- Mortality

Safety

The safety of the IrriSept irrigation unit will be assessed through the clinical review and analysis of adverse events.

Randomization

Subjects who meet all inclusion and exclusion criteria will be centrally randomized in the OR in a 1:1 ratio to either the study product group or the control group, in accordance with a computer-generated block randomization schedule prepared by a non-study statistician. A unique randomization number and associated treatment assignment will be made using an interactive web-based response system (IWRS). Randomization will be stratified by center with no center allowed to enroll more than 120 subjects.

Statistical Methods

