It is anticipated that treatment groups will be well balanced with respect to baseline and demographic characteristics as well as risk factors for SSI, however if there are imbalances these will be accounted for in a supportive analysis using logistic regression. In these analyses, a logistic regression model with treatment as a fixed categorical variable and key baseline/demographic variables that are imbalanced will be included in the model to obtain adjusted estimates of the treatment effect in the form of odds ratios with two-sided 95% confidence intervals. Identification of variables to include will be based on comparisons between the two groups using appropriate two-sided tests based on the underlying distribution of the data. Those variables that are found to be significant (p < 0.05) will be included in the model.

Secondary Endpoints

The rate of readmission within 30 days from the date of the abdominal surgical procedure will be analyzed using the same methods as described for the primary endpoint.

The length of stay in the hospital will be calculated as the difference between the date of discharge and the date of admission, plus 1 day. Length of stay will be summarized by treatment group using descriptive statistics. As length of stay data tends to be highly skewed, a comparison of the LOS between the two treatment groups will be made by modeling the log LOS using a mixed effect model with a fixed effect term for treatment and a random component for center. This means and 95% confidence intervals for the difference between treatment groups will be back transformed and presented along with the two-sided p-value from a two-sample t-test.

An additional analysis will seek to define risk-adjusted length of stay outliers and whether there are observed differences between the two study populations. Using the post-operative length of stay as the dependent variable, a linear model will be used by employing those patients in the study who had no complications identified through the entire 30 day postoperative period. Again, hospital variables will be used. The observed length of stay for all patients will then be compared to the expected length of stay from the model to determine

Study Number IRR-CT-901-2013-01	Version: 1.0	01AUG2014
© Confidential IrriMax Corporation		Page 29 of 35

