Univariate assessment of categorical risk factors and of continuous risk factors will be assessed to identify whether differences exist between the two populations of patients in the frequency of independent variables following patient randomization. Risk factors with P<0.05 on univariate analysis will then be used to create a forward stepwise logistic regression model to predict SSI. Hospital dummy variables will be employed to remove hospital effects. Logistic coefficients will be defined for the clinical variables including the use of the IrriSept irrigation system. Odds ratios and confidence intervals will be established to evaluate statistical significance, or lack thereof, of the IrriSept system. An additional benefit of this modeling will be the development of risk equations that combine administrative, clinical, and laboratory data into the prediction of SSI in this population of patients.

Multiplicity

As there is a single primary endpoint, and no formal unblinded interim analyses that will utilize the primary endpoint to modify the trial, no adjustment for multiplicity is planned. No adjustment for multiplicity is planned for the analysis of secondary endpoints

Sub-groups

To determine whether the treatment effect is consistent across various subgroups, the estimate of the odds ratio (and 95% CI) for the primary endpoint will be estimated and displayed using forest plots for the following sub-groups:

- Age category (≤65 vs. >65 years)
- Gender (female, male)
- Emergency laparotomy for trauma exclusively vs. laparotomy for emergency general surgery

For the analysis of each sub-group, a logistic regression model for the primary endpoint will be used, with terms for treatment group, the sub-group and the sub-group by treatment interaction. The odds ratios and 95% CI's within each sub-group category will be reported, along with the p-value for the interaction term.

Safety Analyses

All safety analyses will be presented using the safety analysis set. No formal hypothesis testing will be conducted.

Adverse Events

Adverse events will be coded using MedDRA (Version 17.x). All AEs that occur after the start of surgery (cut time) will be summarized using frequency counts and percentages. Summaries will be presented by treatment

Study Number IRR-CT-901-2013-01	Version: 1.0	01AUG2014
© Confidential IrriMax Corporation		Page 30 of 35

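### Randomisation and the primary test are stratified by centre, but the risk-difference CI and the supportive and subgroup logistic models are specified without centre

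*Combined protocol and SAP*

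**What the plan says.** The Randomization section states: "Randomization will be stratified by center with no center allowed to enroll more than 120 subjects". The Protocol Synopsis plans 12 to 14 centres.

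Under Efficacy Analyses, Primary Endpoint, SSI counts and proportions are summarised by arm, "along with the difference and 95% confidence interval for the difference (based on the Wald method"). Site is not mentioned there. The formal comparison follows: "A comparison between treatment groups will be made using the Cochran-Mantel-Haenszal test, stratified by site". Then: "The two-sided p-value, the adjusted relative risk (IrriSept/Control) and 95% confidence interval of the relative risk (based on the Wald method) will be reported". Success depends on the two-sided p-value alone. Under Secondary Endpoints, readmission uses the same methods as the primary endpoint.

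The supportive analysis in the same section is "a logistic regression model with treatment as a fixed categorical variable and key baseline/demographic variables that are imbalanced will be included in the model". Covariates enter if they differ between arms at p < 0.05. The Sub-groups section gives odds ratios from a logistic model "with terms for treatment group, the sub-group and the sub-group by treatment interaction". Neither model names centre.

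Centre does appear elsewhere: as a random component in the log length-of-stay model, as hospital variables in the length-of-stay outlier and cost models, and as hospital dummies in the exploratory stepwise SSI model.

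**The concern.** When centre is a randomisation stratum, analyses of the primary endpoint should normally reflect it. Here the test and the relative risk do; the other planned displays of the SSI effect, apart from the exploratory stepwise model, do not.

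Three things follow.

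- The unstratified standard error of the difference carries between-site variation that the design has balanced out, so the interval is somewhat too wide.
- The difference interval and the CMH p-value use different variances. The report could show a successful test beside a difference interval that includes zero.
- A logistic odds ratio that omits a prognostic centre effect estimates a different quantity from one conditional on centre. The supportive and subgroup results then have a different conditioning from the primary analysis.

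The supportive model's entry rule does not repair this. Blocked randomisation within centre balances centre by design, so a p < 0.05 imbalance screen will almost never admit it.

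**Working it through.** **The plan's own figure.** With 300 per arm and a two-sided 5% chi-square test, 20% versus 10% gives 93.1% power against the stated 93%. All nine cells of Table 2.1 reproduce. Nothing below changes the planned size.

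**Unstratified interval at the design effect.** SE = sqrt(0.20×0.80/300 + 0.10×0.90/300) = 0.0289. The 95% CI is −0.100 ± 1.96×0.0289 = −0.157 to −0.043.

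**Excess width, by formula.** For a pooled rate p and between-site variance V of the rate, the ratio of unstratified to stratified SE is about sqrt[p(1−p) / (p(1−p) − V)]. With p = 0.15 (the average of 20% and 10%), p(1−p) = 0.1275. The site SD is an assumption:

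| Site SD (points) | V | SE ratio |
|---|---|---|
| 5 | 0.0025 | sqrt(0.1275/0.1250) = 1.010 |
| 8 | 0.0064 | sqrt(0.1275/0.1211) = 1.026 |
| 10 | 0.0100 | sqrt(0.1275/0.1175) = 1.042 |

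**Excess width, by simulation.** Assumptions: 13 equal centres, 23 per arm each (299 per arm), control rate 20%, treated rate 10%, common odds ratio within centres, 20,000 trials per scenario. The between-centre SD is on the logit scale.

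| SD | Control rates by centre | CI width, unstratified / stratified | SE ratio | Coverage, unstratified / stratified |
|---|---|---|---|---|
| 0 | 20% | 0.113 / 0.113 | 0.998 | 95.1% / 95.2% |
| 0.5 | 8–37% | 0.113 / 0.111 | 1.015 | 95.2% / 94.9% |
| 1.0 | 3–55% | 0.113 / 0.107 | 1.061 | 96.1% / 95.0% |

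**How often CMH gives p < 0.05 while the unstratified Wald CI includes zero** (same layout, 40,000 trials per scenario):

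| True rates | SD 0 | SD 0.5 | SD 1.0 |
|---|---|---|---|
| 20% vs 10% | 0.02% | 0.3% | 1.1% |
| 20% vs 12% | 0.05% | 0.7% | 3.0% |
| 20% vs 14% | 0.04% | 1.0% | 4.4% |

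A repeat with a different seed gave the same pattern; the largest cell was 4.8%.

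**Odds ratio with and without centre.** At 20% versus 10% the odds ratio ignoring centre is (0.10/0.90)/(0.20/0.80) = 0.444. The centre-conditional odds ratio giving the same overall rates is 0.434 at SD 0.5 and 0.403 at SD 1.0. Omitting centre moves the estimate toward 1.

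**Does a stratified interval agree exactly with CMH?** No. In the same layout, a Mantel-Haenszel difference with the Sato variance still disagrees with CMH in about 0.1% to 0.5% of trials. Simple plug-in stratum variances disagreed in about 0.5% to 2%, now with the interval excluding zero when p ≥ 0.05. With 23 per arm per stratum, dividing by n rather than n−1 alone shrinks the SE by a factor sqrt(22/23) = 0.978. The variance therefore has to be named.

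**The case against.** The strongest reply is that the difference interval is descriptive. It sits in the sentence that summarises proportions, and the comparison proper already pairs a stratified test with an adjusted relative risk and its interval. A crude difference beside crude proportions is ordinary reporting. This stands, and it rules out a tempting stronger reading: that the trial's headline interval is mis-specified or that its conclusion is at risk. The documents give the difference interval no role in the success rule.

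A reader might also infer that subgroup effects should be site-stratified relative risks. The documents do not support that. The stated aim is consistency across subgroups through an interaction test, for which odds ratios are natural, and the plan does not say that an overall relative risk appears in the forest plot. Stratified relative risks would also be unstable in small subgroups. One subgroup is age over 65 in a trial capped at 70. If 5% to 10% of 600 patients fall there (assumed), that is 30 to 60 patients, or about 2 to 5 per site across 13 sites.

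Two further replies carry less weight. The exploratory SSI model has hospital dummies, so one centre-adjusted treatment odds ratio is already planned; but that is a separate stepwise analysis and does not alter the supportive or subgroup models. A separate SAP with further detail is promised before first enrolment and could add centre. The plan is silent on centre in these analyses and does not exclude it, but the methods as written leave it out.

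**Conclusion.** The point holds as a minor inconsistency. The difference interval for SSI and readmission, the supportive model and the subgroup models do not reflect the factor used to randomise.

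The interval is conservative, by about 1% to 6% in its standard error. Contradiction with a significant CMH result is possible but uncommon. Those sizes rest on assumed between-site variation and equal centres. With no site variation the effect disappears. The difference in conditioning between the logistic odds ratios and the primary analysis is a matter of specification; its size again depends on site variation.

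The point does not reach the primary p-value, the success rule, the sample size, the adjusted relative risk or the log length-of-stay model. A reader might infer that the plan ignores centre altogether; its use in the primary test and in several other models shows otherwise.

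**What to change.** - **Risk difference, SSI and readmission:** report the site-stratified Mantel-Haenszel difference with a 95% CI from a named variance suited to small strata, such as Sato. The crude proportions can stay as description.
- **Supportive logistic model:** include centre whatever the p < 0.05 imbalance screen shows.
- **Subgroup models:** include centre as a random or conditional effect, keep the odds-ratio scale, and show in the forest plot the overall odds ratio from the same type of model.
- **Small centres:** state a pooling rule in advance.

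The cost is a few lines of SAP text and code, with no change to sample size or data collection. The downside is small: the pooling rule must be chosen, and the interval and the CMH test will still disagree in rare borderline cases. Because the trial is open-label, these choices belong in the SAP before the first patient is enrolled.
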